3.9 Pharmacokinetics (PK)

Individual and mean MEDI8897 serum concentrations for each nominal sampling time will be listed, summarized and plotted versus time. Pharmacokinetic parameters will be listed for each subject and summary descriptive statistics will be presented. Individual and mean T_{max} , C_{max} , C_{150} , AUC_{0-150} , and AUC_{0-last} will be graphically illustrated by ADA status and MA-LRTI outcome. The details of the analyses and presentation of these data will be included in a separate PK report.

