had no effect on PK or the safety profile. These results demonstrated an acceptable safety profile for MEDI8897.

The Phase 1b/2a first-in-pediatric study (D5290C00002) is an ongoing, randomized, double-blind, placebo-controlled, dose-escalation study designed to evaluate the safety and tolerability, PK and ADA for MEDI8897 in healthy preterm infants of 32 - 35 wGA who would not receive RSV prophylaxis based on the AAP ([American Academy of Pediatrics Committee on Infectious Diseases, 2014](#)) or any other local or national recommending bodies' guidelines. This study population was selected based on advice from the United States Food and Drug Administration (US FDA) to perform initial clinical evaluations of MEDI8897 in a population where the benefit of RSV prophylaxis has been proven. Enrolment and dosing have been completed in 89 infants from sites in the United States, Chile, and South Africa. Infants were randomized and received a single IM dose of 10 mg, 25 mg, or 50 mg MEDI8897 (N = 71) or placebo (N = 18). All subjects are being followed for 1 year. The first interim analysis was conducted 30 days (October 2015) after the last subject was dosed to evaluate MEDI8897 serum concentrations, ADA, and safety. At the interim analysis, 1 infant in the placebo group had been withdrawn from the study because the mother could no longer bring the infant in for follow-up visits. At study entry, infants had a mean age (\pm SD) and mean weight (\pm SD) of 6.95 (\pm 2.63) months and 7.31 (\pm 1.84) kg in the placebo group and 6.50 (\pm 2.64) months and 6.82 (\pm 1.90) kg in the MEDI8897 group. MEDI8897 serum concentrations were consistent with the expected extended $t_{1/2}$ in infants. Model-based simulations predict the MEDI8897 median $t_{1/2}$ to range from 83 to 94 days for the 50 mg dose in infants with normal clearance. In healthy preterm infants the safety profile of MEDI8897 was favorable with similar proportions of AEs reported in the placebo (12/18, 66.7%) and MEDI8897 (51/71, 71.8%) recipients. No safety signals were observed with the ascending dose levels. There was 1 serious adverse event (SAE) that occurred in an infant who received 25 mg of MEDI8897. The infant was hospitalized for LRTI and, upon subsequent testing, was found to be negative for RSV by the real time reverse transcriptase-polymerase chain reaction (RT-PCR) assay. The illness resolved. All of the AEs were Grade 1 or 2 in severity. The most frequently reported AEs were URTI (placebo, 7/18, 38.9%; MEDI8897 27/71, 38%), anemia (placebo 5/18, 27.8%; MEDI8897, 9/71, 12.7%), cough (placebo 2/18, 11.1%; MEDI8897, 9/71, 12.7%), pyrexia (placebo 0, MEDI8897, 8/71, 11.3%), bronchiolitis (placebo 5.6%, MEDI8897 7/71, 9.9%), and rhinorrhea (placebo, 1/18, 5.6%; MEDI8897 7/71, 9.9%). There were no AESIs, NOCDs, or deaths. ADA levels at the 30-day interim analysis were similar for placebo and MEDI8897 recipients, with rates of 12.5% (2/18) and 4.4% (3/71) for placebo and MEDI8897 recipients, respectively. A second interim analysis is planned for 6 months after the last subject was dosed (March 2016) to evaluate MEDI8897 serum concentrations, ADA, and safety.

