- Increased respiratory rate at rest (age < 2 months, ≥ 60 breaths/min; age 2–6 months, ≥ 50 breaths/min; age > 6 months – 2 years, ≥ 40 breaths/min) OR
- Hypoxemia (in room air - oxygen saturation < 95% at altitudes ≤ 1800 meters or < 92% at altitudes > 1800 meters), OR
- Clinical signs of severe respiratory disease (eg, acute hypoxic or ventilatory failure, new onset apnea, nasal flaring, intercostal, subcostal or supraclavicular retractions, grunting) or dehydration secondary to inadequate oral intake due to respiratory distress (need for intravenous fluid).

A study schematic is presented in [Figure 3.1.1-1](#).

PK and ADA samples will be collected during screening, on Day 91, 151 and 361 and at hospitalization for LRTI
Safety assessments will be performed from screening through Day 361
* Screening and Day 1 visits may occur on the same day

Figure 3.1.1-1 Study Flow Diagram

ADA = anti-drug antibody; IM = intramuscular; N = number; PK = pharmacokinetic

The endpoints to be measured in this study are described in Section 2.2.

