3.2.3 Rationale for Endpoints

MEDI8897 is being developed to provide RSV immunoprophylaxis for all infants entering their first RSV season. The primary endpoint will examine the efficacy of MEDI8897 compared to placebo in preventing LRTI due to RSV. Respiratory syncytial virus results in a significant burden of disease consisting of hospitalization, visits to the ER, and visits to outpatient clinics. This primary endpoint is designed to allow the capture of this total burden of disease and the efficacy of MEDI8897 in reducing that burden.

A separate secondary endpoint of RSV hospitalization, which would indicate the most serious illnesses, will also be evaluated. Additionally, descriptive statistics of the serum concentrations of MEDI8897 at selected time points will be evaluated as a secondary endpoint and to confirm that serum concentrations are maintained above the target value of

6.8 µg/mL for 5 months. The serum concentration data will be used to characterize the PK of MEDI8897 in infants using a population PK approach. For infants who require hospitalization for LRTI, an additional serum sample for measurement of MEDI8897 concentration and ADA will be obtained around the time of hospitalization. Exposure-response analysis will be performed to relate MEDI8897 serum concentrations and efficacy endpoints (LRTI including RSV-associated hospitalization).

To determine the duration of MEDI8897 serum levels post dosing and to correlate with the development of ADA, serum concentrations will be measured at 360 days post dosing. ADA will be measured at selected time points throughout the study and at 360 days post dosing, when MEDI8897 levels are expected to be low and to not interfere with detection of ADA, if present.

Exploratory endpoints will examine magnitude of healthcare resource utilization and caregiver burden due to RSV illness in the current population. This will allow the determination of social and economic resources that are required for infants who have LRTI.

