4.2.2 Treatment and Follow-up Period

The day of dosing is Day 1 of the study. [Table 4.2.2-1](#) shows all procedures to be conducted on day of dosing and during the follow-up period. Assessments should be performed in the order shown in the table.

Table 4.2.2-1 Schedule of Treatment Period and Follow-up Period Study Procedures

Study Period	Treatment Period	Follow-up Period										LRTI
		V2	V3	V4	V5	V6	V7	Telephone Call	Telephone Call			
Visit Number	Day 1		Day 8 (\pm 2 days)	Day 31 (\pm 5 days)	Day 91 (\pm 7 days)	Day 151 (\pm 7 days)	Day 361 (\pm 7 days)	Q2W from Day 1 to Day 151 (\pm 5 days)	Monthly after Day 151 to Day 361 (\pm 5 days)		As needed	
Medical history update	X	X	X	X	X	X	X					
Physical examination (abbreviated)	X	X	X	X	X	X	X					
Weight	X	X	X	X	X	X	X					
Vital signs	X ^a	X	X	X	X	X	X					
PK blood sample				X	X	X	X				X ^b	
ADA blood sample					X	X	X				X ^b	
Assessment of AEs/SAEs	X	X	X	X	X	X	X					
Assessment of AESI and NOCDs	X	X	X	X	X	X	X					
Concomitant medications	X	X	X	X	X	X	X					
Verify eligibility criteria	X											
Randomization	X											
Investigational product administration	X											
Assessment of LRTI											X ^b	
Nasal swab collection											X ^b	
Telephone contact								X	X			
HRU ^c											X	

Table 4.2.2-1 Schedule of Treatment Period and Follow-up Period Study Procedures

Study Period	Treatment Period	Follow-up Period							LRTI	
		V3	V4	V5	V6	V7	Telephone Call	Telephone Call		
Visit Number	V2									
Procedure / Study Day	Day 1	Day 8 (± 2 days)	Day 31 (± 5 days)	Day 91 (± 7 days)	Day 151 (± 7 days)	Day 361 (± 7 days)	Q2W from Day 1 to Day 151 (± 5 days)	Monthly after Day 151 to Day 361 (± 5 days)	As needed	

- ADA = anti-drug antibody; AEs = adverse events; AESI = adverse event of special interest; ER = emergency room; HRU = healthcare resource utilization; ICU = intensive care unit; LRTI = lower respiratory tract infection; NOCDs = new onset of chronic disease; OTC = over-the-counter; PK = pharmacokinetic; Q2W = once every two weeks; RSV = respiratory syncytial virus; SAEs = serious adverse events; SID = subject identification; V = visit.
- All vital signs (temperature, blood pressure, heart rate, and respiratory rate) should be obtained within 60 minutes prior to dosing, at 30 minutes (± 5 minutes) and at 60 minutes (± 5 minutes) post dose

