 - Nasal samples will be collected for all LRTI within 2 days and up to 14 days after the diagnosis. PK and ADA samples will be collected only for subjects hospitalized with LRTI within 2 days and up to 14 days following hospitalization.
 - HRU includes admission and duration of hospital and ICU stay, number of subjects who require respiratory support and supplemental oxygen use, duration of respiratory support and supplemental oxygen use, number and type of outpatient visits (eg, ER, urgent care, outpatient clinic), and number and days of prescription and OTC medication

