4.3.4 Pharmacokinetic Evaluation and Methods

Blood will be collected to evaluate the PK of MEDI8897 in serum at screening and on Day 91, Day 151, Day 361 and as needed (PK samples will be collected for subjects hospitalized

with LRTI within 2 days and up to 14 days following hospitalization; see [Table 4.2.1-1](#) and [Table 4.2.2-1](#) for schedule of tests). The concentration of MEDI8897 in serum will be measured by MedImmune using validated assays.

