3.8 Anti-drug Antibodies

The number and percentage of subjects who develop anti-MEDI8897 antibodies will be summarized at each visit by treatment group. For those with a positive assessment, the ADA titer results will also be summarized. The number and percentage of ADA positive samples with specificity to the YTE or neutralizing regions of MEDI8897 will also be summarized.

An additional table will summarize the number and percentage of subjects positive for ADA at baseline (ie, ADA prevalence) and positive at any post-baseline time point (ie, ADA incidence). For those with a positive post-baseline assessment, the percentage who were persistent positive and transient positive will also be presented.

1. Persistent positive is defined as positive at ≥ 2 post-baseline assessments (with ≥ 16 weeks between first and last positive) or positive at last post-baseline assessment
2. Transient positive is defined as negative at last one post-baseline assessment, and positive at only one post-baseline assessment or at ≥ 2 post-baseline assessments (with < 16 weeks between first and last positive)

To evaluate the impact of ADA on efficacy and safety, the primary and the secondary efficacy endpoints, as well as TEAE and SAE by SOC and PT based on MedDRA will be summarized by ADA status in three ways: 1) ADA post-baseline status (ie, at least one post-baseline ADA positive or not); 2) ADA persistent positive status (Yes or No); 3) ADA transient positive status (Yes or No).

The impact of ADA on PK will be included in the PK report as mentioned in Section 3.9.

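### SAP 3.8 and 3.9 do not exclude the extra sample taken only at LRTI hospitalization, so ADA status, and Cmax and AUC if read from observed samples, depend partly on the outcome they are compared with

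*SAP*

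**What the plan says.** **Sampling.** The legend to Protocol Figure 3.1.1-1 states: "PK and ADA samples will be collected during screening, on Day 91, 151 and 361 and at hospitalization for LRTI". Protocol 4.3.4 gives the PK schedule as "at screening and on Day 91, Day 151, Day 361 and as needed", and 4.3.5 gives the same days for ADA. The blood-volume table in 4.3.7 lists four draws of 1.5 mL, 6.0 mL in total. A footnote to Table 4.2.2-1 restricts the unscheduled sample: "PK and ADA samples will be collected only for subjects hospitalized with LRTI within 2 days and up to 14 days following hospitalization". Outpatient LRTI triggers no blood sample.

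**ADA.** SAP version 5, section 3.8, summarizes the primary and secondary efficacy endpoints by three ADA classifications. The first is "ADA post-baseline status (ie, at least one post-baseline ADA positive or not". Nothing limits the assessments that count to scheduled visits.

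**PK.** SAP version 5, section 3.9, lists PK parameters for each infant. Individual and mean Tmax, Cmax, C150, AUC0-150 and AUC0-last "will be graphically illustrated by ADA status and MA-LRTI outcome". It does not say how these parameters are obtained and leaves the details to a separate PK report. Protocol 4.8.5.1 names non-compartmental analysis for the half-life only, where the data allow it. Protocol 3.2.3 says the concentration data "will be used to characterize the PK of MEDI8897 in infants using a population PK approach" and also plans an exposure-response analysis.

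**The concern.** Having an extra sample depends on having been hospitalized with LRTI, which overlaps with the outcomes that define the comparison groups. This matters in two places.

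- Ever-positive ADA status can only rise with the number of samples. If hospitalized infants have one more, ADA-positive infants will include relatively more hospitalized cases even where ADA has no effect on protection.
- With no scheduled sample between dosing and Day 91, an observed Cmax is simply the earliest post-dose level and an observed Tmax is the day it was drawn. A hospitalization sample before Day 91 falls higher on the declining curve, so it raises Cmax and AUC0-150 and moves Tmax earlier.

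The PK artefact makes hospitalized infants look more exposed. That would hide, or even reverse, a true relation between low exposure and failure of prophylaxis.

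**Working it through.** **1. Number of scheduled draws.** 4 × 1.5 mL = 6.0 mL, which reproduces the total in Protocol 4.3.7. A fifth scheduled draw of the same volume would give 7.5 mL. The volume table therefore agrees with the figure legend and with 4.3.4.

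**2. PK inputs.** Half-life: Protocol 1.4 reports model predictions "to range from 83 to 94 days for the 50 mg dose in infants with normal clearance". Dosing is Day 1, so Day 91 is 90 days and Day 151 is 150 days after the dose. Assume that parameters are read from observed samples, with a pre-dose level of zero and linear trapezoids.

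**3. One-phase decline.** C(t) = exp(−kt), k = ln 2 / half-life, initial level 1.

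| | half-life 83 d | half-life 94 d |
|---|---|---|
| C(30), C(90), C(150) | 0.778, 0.472, 0.286 | 0.802, 0.515, 0.331 |
| True AUC0-150 = (1 − C(150))/k | 85.5 | 90.7 |
| Observed, no extra sample = 45·C(90) + 30·[C(90)+C(150)] | 43.9 (51% of true) | 48.5 (53% of true) |
| Observed, extra sample at 30 d = 15·C(30) + 30·[C(30)+C(90)] + 30·[C(90)+C(150)] | 71.9 | 76.9 |
| AUC ratio, extra / no extra | 1.64 | 1.58 |
| Cmax ratio = C(30)/C(90) = 2^(60/half-life) | 1.65 | 1.56 |

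**4. With absorption.** The documents give no infant Tmax, so true peaks at 3, 7 and 14 days are assumed, with C(t) proportional to exp(−kt) − exp(−ka·t) and ka set to give that peak. Without an extra sample, observed Cmax is 49-59% of true Cmax and observed AUC0-150 is 52-56% of true. For the same infant with one extra sample:

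| Day of extra sample (post dose) | Cmax ratio | AUC0-150 ratio |
|---|---|---|
| 10 | 1.66-1.95 | 1.74-1.89 |
| 30 | 1.56-1.65 | 1.58-1.64 |
| 60 | 1.25-1.28 | 1.28-1.30 |
| 75 | 1.12-1.13 | 1.14 |
| 110 | 1.00 | 0.99 |

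C150 comes from a scheduled sample and does not change.

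**5. ADA, illustration only.** Take 4.4% positive per sample, the MEDI8897 rate that Protocol 1.4 reports at the 30-day interim of the Phase 1b/2a study. (It is printed beside 3/71, which is 4.2%; the difference is immaterial here.) If samples were independent, the chance of being ever positive is 1 − 0.956³ = 12.6% with three samples and 1 − 0.956⁴ = 16.5% with four, a ratio of 1.30. If results within an infant were perfectly correlated, the ratio would be 1.0. The documents do not say where between these the truth lies.

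**6. If a Day 31 PK sample exists.** In the text available, the "PK blood sample" row of Table 4.2.2-1 has four scheduled marks against three for ADA, and the extra one appears to line up with Day 31. The table layout is damaged, so this needs checking in the source file. With such a sample, a hospitalization at day 10 would raise one-phase Cmax by only 2^(20/94) to 2^(20/83), that is 1.16 to 1.18 times, and a hospitalization after Day 31 would not raise it. The ADA point would be unchanged.

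**The case against.** A reader might infer that the exposure comparison in 3.9 is wrong and biased by outcome. The documents do not establish that. The bias needs parameters read from raw samples, and no document says so. Non-compartmental analysis is assigned only to half-life, and SAP versions 4 and 5, which add Cmax and AUC, no longer contain that sentence. Population PK is planned in Protocol 3.2.3. This objection stands. What remains is that nothing links the population model to the parameters in 3.9, so a programmer could take them from observed data and still comply with the SAP.

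Other limits also stand:

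- Section 3.9 splits PK by ADA status and by LRTI outcome separately. It does not compare ADA with LRTI outcome; the ADA-by-efficacy summary is in 3.8.
- Only a hospitalization sample before Day 91 distorts Cmax. Outpatient cases have none, while infants hospitalized with non-RSV LRTI do. Section 3.9 does not say whether MA-LRTI means RSV only. The shift in a group mean would therefore be smaller than the per-infant ratios and cannot be calculated from the documents.
- Protocol 3.2.3 implies that circulating drug can interfere with ADA detection, so an early hospitalization sample may add fewer positives than the illustration suggests.
- The displays carry no test, alpha or decision rule.

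**Conclusion.** The point holds in a limited form. For ADA, the rule as written in 3.8 makes the grouping variable depend partly on the outcome. The direction is clear and the size is unknown; 1.30 is an illustration and not an estimate. For PK, the firm defect is that 3.9 states neither the derivation nor the handling of hospitalization samples. If the parameters are observed values, hospitalization before Day 91 alone multiplies an infant's Cmax by about 1.1 to 1.95 and AUC0-150 by about 1.1 to 1.9, given a half-life of 83-94 days, an assumed peak at 3-14 days and no scheduled sample before Day 91.

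A reader might also infer that the hypothesis of adequate half-life gets no valid answer. That does not follow: C150 and the concentrations at nominal visits are planned summaries, and the scheduled samples are not outcome-dependent. The primary efficacy analysis is unaffected, as is the test of RSV hospitalization.

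**What to change.** - **SAP 3.8:** for the summaries of efficacy by ADA status, define that status from scheduled-visit samples only.
- **SAP 3.9:** show Cmax and AUC by MA-LRTI outcome only as individual estimates from the population-PK model already planned in Protocol 3.2.3. Omit observed Tmax and Cmax. Compare observed concentrations by outcome at scheduled visits only. State whether MA-LRTI is RSV-confirmed or of any cause.
- **Both:** list hospitalization samples separately.
- **Protocol:** reconcile the possible Day 31 PK mark in Table 4.2.2-1 with the figure legend, 4.3.4 and 4.3.7.

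The cost is SAP wording and a check of one table; no new data are needed. A few unscheduled samples leave the descriptive comparison. Model-based Cmax will still rest largely on the model and prior data, since little is sampled early, and the PK report should say so.
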